**Randomized controlled trial of social cognition interaction training
and a therapeutic alliance focused therapy among persons with
Schizophrenia.**

Clinicaltrial.gov ID NCT02380885

Scientific background

Schizophrenia is associated with impairments in both interpersonal and intrapersonal functioning, which in turn, hinders quality of life (QoL). These impairments are so extensive that various clinicians and researchers view them as a major feature of schizophrenia characterized by difficulties in understanding the social environment and the individual's place within it (Penn, Corrigan, Bentall, Racenstein, & Newman, 1997; Stanghellini, 2000). These impairments are relatively non-responsive to antipsychotic medications (Bellack, Schooler, & Marder, 2004) and are reported by patients as their greatest unmet need (Coursey, Keller, & Farrell, 1995; Middelboe et al., 2001). One strong mediator of social functioning impairments in schizophrenia is disturbance in social cognition (i.e., the cognitive processes that underlie social interaction; Couture, Penn, & Roberts, 2006; Brüne, Abdel-Hamid, Lehmkämper, & Sonntag, 2007). The growing recognition of the devastating impact of social cognition deficits in schizophrenia, have generated attempts to develop interventions that target social cognition as a means to improve social functioning and QoL. One such intervention is Social Cognition and Interaction Training (SCIT; Roberts, Penn, & Combs, 2006). SCIT is a manualized, group-based intervention that has demonstrated efficacy in improving social cognition and social functioning in both inpatient and outpatient samples (Combs et al., 2007a; Combs et al., 2009b; Roberts & Penn, 2009; Roberts, Penn, Labate, Margolis, & Sterne, 2010). SCIT was developed to address the three core domains of social cognition that are disrupted in schizophrenia: emotion perception, theory of mind, and attributional style. The major theoretical assumption underlying SCIT is that schizophrenia is associated with a number of social cognitive distortions and impairments. These include jumping to conclusions (Garety, Hemsley, & Wessely, 1991), attribution bias (Bentall, 1994), as well as problems with Theory of Mind (ToM; Frith, 1992) and emotion perception. Because these cognitive impairments are linked to the mental operations underlying social interactions, such as the human ability and capacity to perceive the intentions and dispositions of others (Brothers, 1990), they interfere with social QoL and functioning.

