
The proposed study assessed both the theoretical assumptions and the effectiveness of the SCIT intervention with persons diagnosed with schizophrenia. The SCIT intervention emphasizes a set of techniques designed to ameliorate the social cognitive deficiencies and biases to promote change. Accordingly, this study will assess both potential mediating processes, such as emotion perception and ToM, that are thought to be limited and distorted by schizophrenia, as well as social functioning and QoL. To test whether any positive change can be attributed specifically to SCIT, we compared its impact to a different intervention, called Therapeutic Alliance Focused Therapy (TAFT). TAFT is based on the system of observing family therapy alliance (Friedlander, Escudero, & Heatherington, 2006) and focuses on the therapeutic alliance. Both interventions (experimental groups) were compared to control group of treatment as usual (TAU).

Method

Research Setting

The current randomized controlled trial (RCT) was an intervention study that assessed the effectiveness of SCIT versus TAFT in a psychiatric community setting in Israel (Clinicaltrial.gov ID NCT02380885). Data were collected between the years 2014 and 2018. Previous studies

derived from this larger project were conducted on the basis of baseline partial samples of the current study (25, 26). Approval for the study was obtained from the ethics committee of the Department of Psychology at Bar-Ilan University, as well as from two psychiatric hospital committees. After receiving a detailed explanation of the study, all research participants provided written informed consent. Data were collected by an experienced mental health practitioner who was trained to administer.

Statistical Analysis:

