Analyses were computed using Predictive Analytics SoftWare (PASW, Version 25.0). To test whether the groups differed in their baseline scores on the scales and whether there were differences between participants who did and did not complete Time 2 assessments, two-way ANOVAs were performed. To examine improvement in the outcomes (SQoL, FEIT, Faux Pas task, SSPA, and AIHQ), mixed repeated measures ANOVAs were used with time (pre, post) and group (SCIT, TAFT, and TAU) as factors. A mixed repeated-measures ANOVA allows for an examination of the extent to which participants improved over time regardless of group, as well as whether they improved significantly more over time in one group versus the other (group-time interaction). To assess the overall effect sizes, partial eta squared (η^2) was computed with $\eta^2 = .01$ indicating small, $\eta^2 = .059$ medium, and $\eta^2 = .138$ large effects (37). In case of a significant effect, a paired two-sample t test was conducted for each group comparing preand post-results. Effect sizes of paired tests were reported with Cohen's d (37) with $d = .2$, indicating small; $d = .5$, medium; and $d = .8$ large effects. To examine whether the therapeutic alliance was associated with the change in the research variables, we performed a multiple regression, with the difference in each variable (difference between time 1 and time 2) as the dependent variable, and group (0-SCIT, 1-TAFT) and the four dimensions of the therapeutic as the independent variables.

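### With one pre and one post score, the group-by-time test is an unadjusted change-score ANOVA; ANCOVA on data already collected is usually more precise

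*Combined protocol and SAP*

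**What the plan says.** All references are to the combined protocol and SAP. For SQoL, FEIT, Faux Pas, SSPA and AIHQ, the Statistical Analysis section states that "mixed repeated measures ANOVAs were used with time (pre, post) and group (SCIT, TAFT, and TAU) as factors". The model serves two aims: "the extent to which participants improved over time regardless of group", and "whether they improved significantly more over time in one group versus the other (group-time interaction". Baseline scores are compared between groups, and differences are also examined between "participants who did and did not complete Time 2 assessments". No outcome model is said to include the baseline score as a covariate. A significant effect is followed by paired pre-post t tests within each group.

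The alliance analysis is a multiple regression "with the difference in each variable (difference between time 1 and time 2) as the dependent variable, and group (0-SCIT, 1-TAFT", plus four alliance dimensions. It has no baseline term either.

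The Research Setting section describes a randomised trial and states: "Data were collected between the years 2014 and 2018".

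**The concern.** In a randomised three-arm trial, the question of whether one arm improved more than another falls on the interaction. With a single pre and a single post score, that interaction is the change-score comparison. It subtracts the whole baseline score, when the data would usually support subtracting only part of it. The excess is noise, and it lowers power on all five outcomes.

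This is one cost, a loss of efficiency. With equal SDs, a chance baseline imbalance between arms shifts the change-score contrast by −(1−ρ) times the imbalance, where ρ is the pre-post correlation. Averaged over randomisations, that shift is the extra variance, and the ordinary standard error already contains it. Regression to the mean that all arms share cancels in the interaction.

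No other arm term in the section fills the gap:

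- The ANOVA's group main effect averages the pre and post scores, so it targets half of a Time 2 effect.
- The alliance regression's SCIT/TAFT term uses unadjusted differences and leaves out TAU.
- The paired t tests are within-arm.

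**Working it through.** **Inputs.** From the documents: three randomised arms, two time points, five outcomes, no covariate. Not in the documents, and so assumed: ρ, the pre and post SDs (s0, s1), arm sizes (n per arm), effect size and a 5% test level. ρ may differ across the five scales. The plan states no power or precision figure to reproduce. All figures take data as complete and independent.

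**1. Identity.** On simulated data with arms of 20, 17 and 23, the mixed-ANOVA interaction gives F = 0.352976 on 2 and 57 df. The one-way ANOVA of post minus pre gives the same F.

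**2. Variance of an arm contrast under a common slope (large samples).**

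- Change score: proportional to s0² + s1² − 2ρ·s0·s1
- ANCOVA: proportional to s1²(1 − ρ²)
- Difference: (s0 − ρ·s1)², never negative

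With s0 = s1 = 1 the difference is (1−ρ)² and the proportional cut is (1−ρ)/2. Estimating the slope costs a factor 1 + 1/(3n−5), which is 1 + 1/40 = 1.025 at 15 per arm and 1 + 1/85 = 1.012 at 30.

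| ρ | Change | ANCOVA | Difference | Cut, large sample | CI narrower by | Cut, 15 per arm | Cut, 30 per arm |
|---|---|---|---|---|---|---|---|
| 0.3 | 1.40 | 0.91 | 0.49 | 35% | 19% | 33% | 34% |
| 0.5 | 1.00 | 0.75 | 0.25 | 25% | 13% | 23% | 24% |
| 0.7 | 0.60 | 0.51 | 0.09 | 15% | 8% | 13% | 14% |
| 0.9 | 0.20 | 0.19 | 0.01 | 5% | 3% | 3% | 4% |

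Break-even for equal SDs is ρ = 2/factor − 1: 0.951 at 15 per arm and 0.977 at 30.

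**3. Unequal SDs.** The ANCOVA/change variance ratio is s1²(1−ρ²)/(s0² + s1² − 2ρ·s0·s1).

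- s1/s0 = 0.8, ρ = 0.5: 0.48/0.84 = 0.571, a 43% cut.
- s1/s0 = 1.25, ρ = 0.5: 1.172/1.3125 = 0.893, an 11% cut.
- s1/s0 = 1.25, ρ = 0.7: 0.797/0.8125 = 0.981, a 2% cut.
- s1/s0 = 1.25, ρ = 0.8: 0.5625/0.5625 = 1.00, no gain, because the true slope ρ·s1/s0 is then 1.

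At 15 per arm the last two ratios become 1.005 and 1.025.

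**4. Power of the overall three-arm test** (simulated, 4,000 trials per setting, equal SDs, one arm 0.6 SD better), change score vs ANCOVA:

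| ρ | 15 per arm | 30 per arm |
|---|---|---|
| 0.3 | 26% vs 38% | 50% vs 69% |
| 0.5 | 36% vs 46% | 67% vs 79% |
| 0.7 | 55% vs 61% | 87% vs 92% |
| 0.9 | 97% vs 97% | 100% vs 100% |

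Type I error of both tests was 4.3% to 5.9%.

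**5. Supporting checks (simulated).**

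- Group main effect: mean estimate 0.497 for a true Time 2 effect of 1.0.
- Shared regression to the mean (all arms sampled low, ρ = 0.5): within-arm gain 0.405 SD, between-arm contrast 0.002.

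**6. Alliance regression.** With alliance unrelated to baseline and 15 per arm, adding baseline gives variance ratios for the SCIT/TAFT term of 0.697, 0.772, 0.883 and 1.004 at ρ = 0.3, 0.5, 0.7 and 0.9. The alliance coefficients can also move. Suppose one dimension correlates r = 0.3 with baseline (assumed) and has no effect on Time 2 given baseline. Its coefficient on unadjusted post-minus-pre change is then −(1−ρ)·r = −0.21, −0.15, −0.09 and −0.03 SD.

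**7. Unequal slopes.** For SCIT minus TAFT with equal allocation, the variance from slope mismatch, in units of s0²/n, sums (arm slope − fitted slope)² over the two arms. The fitted slope is the pooled value for ANCOVA and 1 for the change score.

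- Slopes 0.7/0.5/0.3 (SCIT/TAFT/TAU): ANCOVA 0.2² + 0² = 0.04; change score 0.3² + 0.5² = 0.34.
- Slopes 1/1/0: ANCOVA (1/3)² + (1/3)² = 0.22; change score 0.

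**The case against.** The strongest reply is that nothing is broken. The interaction test is unbiased under randomisation and holds its type I error. The trial is finished, so a new analysis cannot replace the planned one. All of this is true, and it limits the point to precision.

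A second reply is that the gain may be small or absent. The break-even correlations of 0.95 and 0.98 hold only for equal SDs. With a post/pre SD ratio of 1.25 the gain has gone by ρ of about 0.7 to 0.8, an ordinary range. This stands and belongs in any account of the size. The loss from using ANCOVA there is at most about 2.5% of variance at 15 per arm, against possible gains of 25% or more elsewhere.

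Third, the advantage needs a common slope, and the 1/1/0 example shows that change scores can win. This also stands, and it is why an arm-by-baseline model belongs beside the ANCOVA.

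Fourth, the section names no primary test, so calling the interaction the main arm comparison is an inference. It is a fair one: the interaction is the only term that compares improvement across all three arms.

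Fifth, the SCIT/TAFT term is a side term in the alliance regression, whose stated purpose is the alliance association. That is correct. For that model the possible shift in the alliance coefficients matters more than the variance figure.

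**Conclusion.** The concern holds. The interaction is a change-score ANOVA with no baseline adjustment, and under a common slope ANCOVA is at least as precise in large samples and usually more so. With equal SDs and ρ from 0.3 to 0.9, the loss is 35% down to 5% of contrast variance. In the assumed 15-per-arm example, that is 12 percentage points of overall power at ρ = 0.3 and none at 0.9. With unequal SDs the cut at ρ = 0.5 runs from 43% to 11%, and it reaches zero where the true slope is 1.

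These sizes rest on assumed correlations, SDs, arm sizes and effect, and on complete, independent data. Time 2 dropout and clustering (the Scientific background section says "SCIT is a manualized, group-based intervention") are separate matters that ANCOVA does not settle. The conclusion concerns efficiency only; it gives no reason to call the planned test biased.

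**What to change.** - For each of the five outcomes, estimate arm effects by ANCOVA of the Time 2 score on arm and that outcome's baseline. A mixed model with baseline means constrained equal across arms is an alternative.
- Give the overall arm test first, then adjusted SCIT−TAFT, SCIT−TAU and TAFT−TAU differences with 95% confidence intervals. With three arms this order holds the error rate within an outcome (simulated familywise error, 15 per arm, 6,000 trials: 4.5% with all arms equal, 5.3% with one different). It does not cover the five outcomes together.
- Report an arm-by-baseline model, with baseline centred, as a routine sensitivity analysis and not one triggered by how the data look.
- Add the baseline score to each alliance regression and show both versions. Alliance is not randomised, so its coefficients may change as well as their precision.
- Keep the repeated-measures model for improvement regardless of group, because ANCOVA of Time 2 has no time effect.
- Label all of this as a re-analysis specified after data collection and print it beside the original ANOVA.

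The cost is one degree of freedom per outcome in the ANCOVA and one in each alliance regression, with two more in the sensitivity model. No new data are needed.

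### Uncorrected partial eta squared is graded against fixed cut-offs without an interval; if about 140 or fewer participants are analysed, a null group-time interaction reaches the 'small' cut-off more often than not

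*Combined protocol and SAP*

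**What the plan says.** The Statistical Analysis section names five outcomes, "outcomes (SQoL, FEIT, Faux Pas task, SSPA, and AIHQ". For these, "mixed repeated measures ANOVAs were used with time (pre, post) and group" as the two factors, the arms being SCIT, TAFT and TAU. Whether one arm improved more than another is read from the group-time interaction.

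For size of effect, the section says: "To assess the overall effect sizes, partial eta squared" was computed, and it attaches the words small, medium and large to values of .01, .059 and .138. It mentions no correction for bias and no confidence interval, and it sets no condition on when a label is given. The condition comes in the following sentence and concerns only the follow-up tests: "In case of a significant effect, a paired two-sample t test was conducted for each group".

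The document states no planned or analysed sample size, no alpha and no power.

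**The concern.** Partial eta squared is the share of sample variation assigned to an effect. Arm means always differ a little by chance, so the share is above zero even when the true effect is zero. The excess is larger when there are more arms and fewer participants. A fixed cut-off of .01 takes no account of this, and in a trial of limited size chance alone can carry the statistic past it.

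At stake is how the effect sizes for five outcomes are described. A reader told that an interaction was *small* takes it that a small difference in improvement was observed. If that word is the usual result of no difference at all, it carries little information, and a real small effect is shown as larger than it is.

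**Working it through.** **Inputs from the Statistical Analysis section.** Three arms and two time points; cut-offs .01 and .059; no correction or interval.

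**Inputs not in the documents (assumptions).** Number analysed, N, taken over a range. Alpha .05, used only to compare the cut-off with a significance test. Changes are taken as normal with equal variance across arms. Arm sizes need not be equal for the null results.

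**Step 1: degrees of freedom.** With two time points, the interaction F equals a one-way ANOVA F on change scores. So df1 = (3-1)(2-1) = 2 and df2 = N-3.

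**Step 2: distribution with no true interaction.** Partial eta squared = df1·F/(df1·F + df2), which follows Beta(df1/2, df2/2) = Beta(1, (N-3)/2). Hence:

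- mean = 2/(N-1)
- chance of reaching c = (1-c)^((N-3)/2)

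**Step 3: results under the null.**

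| N analysed | Mean | Chance of reaching .01 | Chance of reaching .059 |
|---|---|---|---|
| 60 | 2/59 = .034 | .99^28.5 = 75% | .941^28.5 = 18% |
| 90 | 2/89 = .022 | .99^43.5 = 65% | .941^43.5 = 7% |
| 120 | 2/119 = .017 | .99^58.5 = 56% | .941^58.5 = 3% |
| 140 | 2/139 = .014 | .99^68.5 = 50.2% | 1.6% |
| 150 | 2/149 = .013 | .99^73.5 = 48% | 1.2% |
| 200 | 2/199 = .010 | .99^98.5 = 37% | 0.3% |
| 300 | 2/299 = .007 | .99^148.5 = 22% | below 0.1% |

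Simulation of 20,000 three-arm trials at each of N = 60, 90, 120 and 150 agreed: means .0341, .0226, .0168 and .0134; chance of passing .01 of 75.2%, 64.7%, 55.3% and 47.5%.

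**Step 4: two separate thresholds.** The mean exceeds .01 when 2/(N-1) > .01, that is N < 201. The chance of reaching .01 exceeds one half when N < 3 + 2·ln(.5)/ln(.99) = 140.9, that is N of 140 or fewer. They differ because the null distribution is skewed to the right. From N = 141 to 200 the mean is above .01, yet most null results fall below it.

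**Step 5: a true value of .01.** Non-central F with noncentrality N × .01/.99 gives an average reported value of .043 at N=60, .032 at N=90, .027 at N=120 and .020 at N=200. Partial epsilon squared, df1(F-1)/(df1·F + df2), averages .010 at each of these sizes when negative values are kept.

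**Step 6: comparison with the test.** At alpha .05, significance requires a partial eta squared of .100 (N=60), .067 (N=90) or .050 (N=120). A value of .01 corresponds to p of .75, .65 and .56 at those sizes.

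**Step 7: what the corrected index does and does not cure.** Under the null, partial epsilon squared averages zero, but it still passes .01 in 28% of trials at N=60, 24% at N=90 and 21% at N=120. If negative values are set to zero, its null mean at N=60 is .013, above .01 again. Restricting labels to significant results does not make the estimate accurate either. At N=60, a null interaction that happens to be significant has mean partial eta squared .0998 + (1-.0998)/(28.5+1) = .130. The matching epsilon squared is 1 - (1-.130)×59/57 = .10, which is *medium* on the plan's scale. So the interval is needed as well as the formula.

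**The case against.** The strongest reply is that no inference is drawn from eta squared. The plan judges whether arms differ in improvement by the significance of the interaction. That F test keeps its nominal error rate whichever index is printed, and the paired tests follow only a significant effect. A value of .01 at N=60 would stand beside a p-value of about .75, and few readers would take that as a benefit. Partial eta squared with conventional benchmarks is also a common and reproducible description. All of this stands, and it makes the point one of reporting.

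Stronger readings are tempting, and the documents do not support them:

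- *The trial is small, so null interactions will usually be labelled.* No sample size is stated, and *usually* needs N of 140 or fewer. The N < 201 condition concerns the mean only.
- *The plan will declare that arms differ when they do not.* A size label is not a finding of difference, and the text neither requires nor excludes labels on non-significant interactions.
- *The effect size is a headline result.* The section says only that it was computed, and gives it no primary role.
- *Small effects are overstated several-fold.* This depends on N: about 4.3-fold at N=60 and 2-fold at N=200 for a true .01. For a true .059 at N=90 the average is .080, about 1.4-fold.

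The bias also matters less for the time main effect, which has one numerator degree of freedom: the null chance of passing .01 is 45% at N=60 and 35% at N=90.

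The reply leaves one thing unanswered. The effect-size sentence is unconditional, and nothing in the plan corrects the estimate or shows its precision.

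**Conclusion.** The point holds as a cheap improvement in reporting, conditional on the number analysed. Below 201 participants, chance alone gives the interaction an expected partial eta squared above the plan's lowest cut-off. At about 140 or fewer, a null interaction reaches that cut-off more often than not. At 300 the null mean is .007 and the chance is 22%, so the problem is then mild. No hypothesis test, error rate or testing sequence in the plan is affected.

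The figures assume normal changes with equal variance across arms; other distributions would alter the exact values. How often a misleading label would appear also depends on whether non-significant interactions are labelled, which the plan leaves open.

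**What to change.** For each effect, report partial epsilon squared, df1·(F-1)/(df1·F + df2), or partial omega squared, in place of raw partial eta squared. Show negative estimates as they are; setting them to zero brings bias back. Give a 90% confidence interval with every estimate. Attach a size label only to a significant effect, and only with its interval beside it. State the number analysed for each outcome, so that the degrees of freedom can be read.

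The cost is one formula and one interval per effect, from F values and degrees of freedom that the planned ANOVAs already produce. No new data are needed and no test changes. The downside is that reported effect sizes become smaller and some are negative, which will need a sentence of explanation.

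### No unadjusted pairwise contrast of change between arms is planned: the three-arm omnibus interaction is followed only by pre-post t tests inside each arm

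*Combined protocol and SAP*

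**What the plan says.** The aims at the end of the Scientific background set SCIT against TAFT, to see whether any benefit belongs to SCIT in particular, and set both interventions against TAU. Research Setting again describes the trial as SCIT versus TAFT.

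The Statistical Analysis section fits, for each of five outcomes, a mixed repeated-measures ANOVA with two time points and three groups. It says this model gives "an examination of the extent to which participants improved over time regardless of group" and also shows "whether they improved significantly more over time in one group versus the other (group-time interaction"). Three further elements matter here:

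- **Follow-up.** "In case of a significant effect, a paired two-sample t test was conducted for each group comparing preand post-results".
- **Effect sizes.** One is global: "To assess the overall effect sizes, partial eta squared" is used. The other belongs to the within-arm tests: "Effect sizes of paired tests were reported with" Cohen's d.
- **Alliance regression.** Change scores are regressed on "group (0-SCIT, 1-TAFT) and the four dimensions of the therapeutic as the independent variables". The stated purpose is "To examine whether the therapeutic alliance was associated with the change in the research variables".

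The section's other ANOVAs concern baseline scores and Time 2 completion, not change.

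**The concern.** The questions are pairwise and the analysis is not. The interaction is a valid randomised comparison, but it tests all three arms jointly. The phrase about one group versus the other fits two arms; here there are three. Once the interaction is significant, the plan moves to tests of change from zero inside each arm, which make no use of the randomised comparison. Significance in one arm and not another does not show that the arms differ, and significance in both does not show that they are alike. The per-arm d values can be set side by side, but no test or interval for their difference is specified.

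The SCIT-TAFT term in the alliance regression does not fill the gap. It is adjusted for alliance, and TAFT is the arm that "focuses on the therapeutic alliance". It also omits TAU. The documents do not say when alliance was measured; if arm could already have affected it, the coefficient is not the total SCIT-TAFT difference. SCIT-TAU and TAFT-TAU have no term anywhere.

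The trigger is also unclear: a significant effect could mean the interaction or the time effect, since the preceding text names both. Under the second reading, the paired tests could be run with no evidence of any difference between arms.

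**Working it through.** **Structure.** Three groups by two times gives (3 - 1) x (2 - 1) = 2 numerator df for the interaction. What the plan specifies for each comparison of change:

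| Comparison | Unadjusted estimate, CI or test | Other |
|---|---|---|
| SCIT-TAFT | none | alliance-adjusted coefficient |
| SCIT-TAU | none | none |
| TAFT-TAU | none | none |

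**Illustration.** There is no planning figure to reproduce. Assumed: equal arms, n = 20, 30, 40 per arm, normal change scores with SD 1, two-sided 5%, and the interaction as trigger; 400,000 simulated trials per scenario. Formulas, with m the mean change in an arm, s its SD and s_p the pooled SD:

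- Interaction: with two time points it equals the one-way F on change, F = n x var(arm means) / s_p², on 2 and 3(n - 1) df, that is 57, 87 and 117 denominator df.
- Within-arm test: t = m / (s/√n), n - 1 df; d = m/s.
- Direct contrast: t = (m_SCIT - m_TAFT) / (s_p √(2/n)), 3(n - 1) df.

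**Scenario 1: SCIT = TAFT = 0.5, TAU = 0 (no true SCIT-TAFT difference)**

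| n per arm | 20 | 30 | 40 |
|---|---|---|---|
| Interaction significant (triggered) | 34% | 49% | 62% |
| Exactly one active arm significant, of triggered trials | 49% | 31% | 18% |
| Same, of all trials | 16.5% | 15.0% | 11.0% |
| Reported d differ by 0.3 or more, of triggered | 52% | 37% | 27% |
| Direct contrast falsely significant, of triggered | 12% | 9% | 8% |
| Same, of all trials | 4.2% | 4.5% | 4.7% |

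A check without the trigger: if p is the power of the paired test, two equally effective arms disagree with probability 2p(1 - p). At n = 20, p = 0.565 gives 2 x 0.565 x 0.435 = 0.49. Varying the common effect over 0.4 to 0.6 SD widens the triggered disagreement range to 6% to 63%.

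**Scenario 2: SCIT = 1.0, TAFT = 0.5, TAU = 0 (a real SCIT-TAFT difference)**

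| n per arm | 20 | 30 | 40 |
|---|---|---|---|
| Interaction significant (triggered) | 79% | 94% | 98% |
| Both active arms significant, of triggered | 57% | 75% | 87% |
| In those trials: SCIT has the larger d | 88% | 95% | 97% |
| In those trials: direct contrast significant | 21% | 39% | 56% |
| Direct contrast significant, of triggered | 42% | 51% | 61% |
| Average 95% CI half-width of the contrast (SD) | 0.63 | 0.51 | 0.44 |

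The half-width is t(0.975) x s_p x √(2/n); at n = 20 this is about 2.00 x 1 x 0.316 = 0.63.

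**Trigger wording.** If all three arms change equally by 0.2 to 0.6 SD, a mixed within-arm pattern follows in 3% to 5% of trials when only the interaction triggers, and in 12% to 73.5% if the time effect triggers too.

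**Alliance-adjusted term.** If TAFT raised alliance by 0.5 SD and alliance predicted change by 0.4 SD per SD (both assumed, with alliance treated as one score), the coefficient departs from the total difference by 0.5 x 0.4 = 0.20 SD. The range is 0.2 x 0.2 = 0.04 to 0.8 x 0.5 = 0.40. If arm had not yet affected alliance when it was measured, there is no such shift.

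**Error of the replacement, within one outcome.** Under the global null, at least one of three unadjusted 95% CIs excludes zero in 12% of trials, 7% with a non-significant interaction. Gating p-values and CIs on the interaction gives 5.0%; ungated Tukey intervals also give 5.0%. The gated SCIT-TAFT error is 4.1% to 4.8% at (0.5, 0.5, 0) and 5.0% to 5.1% at (1.5, 1.5, 0).

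**The case against.** The strongest reply is that the interaction already is a valid between-arm test, and that the documents nowhere claim superiority from the within-arm tests. On that view the follow-up is incomplete rather than the inference invalid. A one-paragraph analysis section may also be silent on contrasts without excluding them, and if arm means and SDs of change are reported, a reader can derive a contrast. The per-arm d values usually show the direction, as scenario 2 confirms. Finally, the data are in, so contrasts added now carry limited confirmatory weight.

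Part of this stands. The interaction is sound, direction is often visible, and severity is open to argument. The illustrations rest on assumed inputs; the scenario 1 percentages of triggered trials are larger than those of all trials; and the trigger and alliance calculations are side issues that the main point does not need.

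The core is untouched. The section is not merely silent about follow-up: it names one, and it is within-arm. Direction without an interval does not answer whether change is specific to SCIT, and the plan does not commit to reporting what a reader would need to build the contrast.

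**Conclusion.** The concern holds, and the plan should be changed. Followed as written, it can establish that some arms differ in change but leaves all three pairwise differences without an unadjusted estimate, interval or test. This conclusion comes from the text alone and needs no assumption.

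Its practical size depends on inputs the documents do not give. Under the assumptions above, equally effective arms can look different in a substantial share of triggered trials, while truly different arms usually both reach significance. In the second case a direct contrast would itself miss the difference in 58%, 49% and 39% of triggered trials. That uncertainty is what a reported interval would show.

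**What to change.** Replace the two sentences on the paired tests and their effect sizes with:

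> For each outcome, the three pairwise between-group differences in change (SCIT-TAFT, SCIT-TAU, TAFT-TAU) are estimated from the same model and reported with 95% CIs and between-group standardised differences. Pairwise p-values and CIs are used for inference only if the group-by-time interaction is significant; otherwise the estimates and CIs are labelled descriptive. Within-group pre-post changes and their Cohen's d are descriptive only, and a time main effect is not evidence of efficacy. These contrasts were added after data collection (2014-2018).

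The text should also name the SD used to standardise the differences and say that error is controlled within one outcome only, not across the five.

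Simultaneous Tukey intervals without a gate are an acceptable alternative, at some cost in power. In scenario 2, over all trials, they detect SCIT-TAFT in about 21%, 33% and 45%, against about 33%, 48% and 60% for gated contrasts.

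The cost is SAP wording and three contrasts per outcome on data already collected. Within-arm results lose inferential status, and the contrasts must be labelled post hoc, which limits how confirmatory they can be.
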